4.4.1.1. CAB LA Q2M

The CAB LA 600 mg Q2M regimen is predicted to achieve concentrations above 1.35 $\mu\text{g}/\text{mL}$, the geometric mean trough concentration (C_{τ}) following oral CAB 10 mg once daily, which was shown to be efficacious in the LATTE study. The lower bound of the 90% prediction interval is approximately 0.166 $\mu\text{g}/\text{mL}$, indicating that 95% of participants on this regimen should remain above the PA-IC₉₀ throughout dosing (Figure 2). The CAB LA Q2M regimen consists of identical 600 mg doses administered at Day 1, Month 2, and Q2M thereafter. Observed data for the optimized Q2M regimen in LATTE-2 Extension Phase were consistent with predictions, with a geometric mean CAB trough concentration of 1.58 $\mu\text{g}/\text{mL}$ 4 weeks following the reduced 600 mg IM loading dose and of 2.03 $\mu\text{g}/\text{mL}$ following the fourth injection.

Figure 2 Simulated* Median (90% Prediction Interval [PI]) CAB Plasma Concentrations versus Time for the Optimized CAB LA Q8W Regimen (600 mg IM Day 1, Week 4, Q8W Thereafter)

*Note: current simulations based on interim plasma concentration dataset

[figure not shown]
A one-week delay in CAB LA dosing for the Q2M regimen at steady state is predicted to result in ~92% rather than 95% of participants achieving trough concentrations above the PA-IC₉₀, which is considered acceptable.

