4.4.1.2. RPV LA Q2M

The RPV LA Q2M regimen for this study (POLAR) was selected based on safety and efficacy data from study 200056 (LATTE-2) and supported by modeling and simulation of pharmacokinetic data obtained following administration RPV LA administration in healthy participants (Phase 1 studies C158, and LAI115428 [GlaxoSmithKline Document Number [2011N112455_03](#)]) and in HIV-infected participants (Phase 2 study LATTE-2), the majority of the data coming from 200056 (LATTE-2).

The RPV LA 900 mg Q2M regimen is predicted to achieve median (90% PI) steady-state C_{τ} of 54 ng/mL (23 – 112 ng/mL) (Figure 3). With this regimen, 100% of participants remain above the RPV protein-adjusted 90% inhibitory concentration (PA-IC₉₀) during the whole dose interval at steady-state. These data are similar to the observed Week 32 median steady-state C_{τ} in LATTE-2 for Q8W which was also 54 ng/mL and the mean C_{τ} was 58 ng/mL. The RPV LA Q2M regimen consists of identical 900 mg doses administered at Day 1, Month 2, and Q2M thereafter. With the second RPV LA dose administered 1 month after the first dose, the anticipated median RPV C_{τ} at Week 4 (prior to second injection) is 40 ng/mL (versus 30 ng/mL observed prior to second injection at Week 8 in LATTE-2, where the RPV LA dose at Week 4 was not included), with >92% of participants above the RPV PA-IC₉₀ of 12 ng/mL. Observed data for the optimized Q2M regimen in LATTE-2 Extension Phase were consistent with predictions, with a geometric mean RPV trough concentration of 49.9 ng/mL 4 weeks following the 900 mg IM loading dose and of 57.5 ng/mL following the fourth injection.

Figure 3 Simulated* Median (90% PI) RPV Plasma Concentrations versus Time Profile for the Optimized RPV LA Q8W regimen (900 mg IM Day)

* Note: current simulations based on interim plasma concentration dataset

At steady-state, a one-week delay in dosing for the RPV LA Q2M regimen is predicted to result in a median steady-state C_{τ} that is approximately 11% lower (48 ng/mL) than for dosing that is administered on schedule, with >99% of subjects still remaining above the RPV PA-IC₉₀. This supports allowance of some flexibility in the dosing regimen similar to what is currently practiced in ongoing LATTE-2 and ATLAS 2M studies.

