6.8.1. IM Dosing

Participants receiving CAB LA and/or RPV LA are anticipated to be at risk for development of virologic resistance if ART is interrupted. The time period during which participants are at risk for development of virologic resistance may be determined by the period between when drug levels fall below therapeutic values and when they fall below levels which exert selective pressure on HIV. This time period will vary by ART agent and is dependent upon effective concentration, inhibitory concentration, and half-life. Plasma concentrations of both LA drugs may be measurable for more than one year following IM injections. Any interruption in IM dosing should be discussed with the Medical Monitor. Investigators should ensure that the participant initiates alternative highly active ART to minimize the risk of developing resistance as concentrations of CAB and RPV decline over time.

IM dosing is expected to occur during the week in which the participant's projected visit falls (as according to the date of the first injection). The first injections for participants from LATTE on oral CAB + RPV will occur at Day 1.

Since the first injection visit (Day 1) will determine the future injection visit schedule for participants, planning for the first injection visit date (within allowed visit windows) should take into consideration the availability of the participants to adhere to future visit windows (planned vacations, business trips, *etc.*).

CAB LA + RPV LA dosing for participants transitioning from oral CAB + RPV is as follows:

All injections should be planned as single injections per drug.

6.8.1.1. IM injections every 2 months (Q2M):

On Day 1, participants will return to the clinic, take the last dose of their oral (CAB 30 mg + RPV 25 mg), and receive the first CAB LA (600 mg) + RPV LA (900 mg) injections (within 2 hours of the final oral dose of CAB + RPV).

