The second loading injection will be administered at Month 2 (CAB LA 600 mg + RPV LA 900 mg, with subsequent injections (CAB LA 600 mg + RPV LA 900 mg) occurring every 2 months thereafter. The dosing window for the second injection allows administration between -7 days of the proposed Month 2 injection visit and the proposed Month 2 injection visit date, but preferably not later than the proposed Month 2 injection visit date. After Month 2, a dosing window (± 7 days) for injections is stipulated. The Medical Monitor must be contacted to discuss individual participant case management if a dose has to be administered outside of the window.

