- k. Q2M Injections are 1 x CAB LA 600 mg IM + 1 x RPV LA 900 mg IM. If possible, injections should be spaced approximately 2 cm from one another and from the site of any previous injection and or any injection site reaction. Bring RPV LA to approximately room temperature prior to injecting. Time and location of injection (right or left) as well as needle length used will be collected in the eCRF. **IM dosing is expected to occur during the month in which the participant's projected visit falls (as according to the Day 1 visit). An additional (+ or -) 7 day window from date of projected visit is stipulated for IM dosing. All decisions regarding dose interruption/ resumption must be discussed with the medical monitor in advance.**
- l. Or Long-Term Follow Up
- m. Follow Up Visit - Conduct ~4 weeks after the last dose of IP if not entering Long-Term Follow Up and only if the participant has ongoing AEs or lab abnormalities at the last on-study visit. May be conducted by telephone.

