8.6.1. Treatment Interruption Due to an Adverse Event

IP may be interrupted at the discretion of the investigator and according to the severity of the AE. If one or more ART medication is held due to toxicity or AEs, all ART medications should be held to reduce the risk of development of resistance taking into account the length of the planned interruptions and the PK half-life of each ART of the regimen, in order to minimize the risk of development of resistance.

No toxicity-related dose reductions of IP will be allowed. IP should be restarted as soon as medically appropriate; in general, for oral dosing, this should be no longer than 14 days after discontinuation (unless Grade 3 or 4 toxicities persist). Any interruption in therapy during the Maintenance Phase, oral dosing, of greater than 7 consecutive days must be discussed with and agreed by the Medical Monitor prior to resumption of therapy. The Medical Monitor must be contacted upon becoming aware of resumption in therapy, if therapy was resumed without prior approval (Section 6.8). **IM dosing is expected to occur during the month in which the participant’s projected visit falls (as according to the first injection visit). An additional (+ or -) 7 day window, from the projected visit date, is stipulated for IM dosing.** Any interruption outside of this guidance MUST be discussed with the Medical Monitor prior to reinitiating IM IP (see Section 6.8.1).

Guidance is provided below on general participant management and IP interruptions based on the severity of the AE. Information regarding permitted substitutions \ is provided in Section 6.7.1.1. All changes in the IP regimen must be accurately recorded in the participant’s eCRF.

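### Injection windows run from Day 1 with no limit from the previous dose, so an in-window gap can reach 74 days, beyond the one-week delay the protocol text addresses and the 67 days after which the SAP counts under-dosing

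*Protocol*

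**What the plan says.** Protocol 6.8.1 fixes the anchor: "Since the first injection visit (Day 1) will determine the future injection visit schedule for participants". The second injection may be up to 7 days early and preferably not late (6.8.1.1; 4.2.2 gives the window as minus 7 days). After that, each injection may fall 7 days either side of its own projected date: "An additional (+ or -) 7 day window from date of projected visit is stipulated for IM dosing" (footnote k, in 1.3 and 8.1.1).

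The Medical Monitor triggers concern departures from the window or interruptions. Section 6.8.1.1 says "The Medical Monitor must be contacted to discuss individual participant case management if a dose has to be administered outside of the window", and 8.6.1 says "Any interruption outside of this guidance MUST be discussed with the Medical Monitor prior to reinitiating IM IP". Footnote k's own closing instruction covers interruption and resumption, not a dose given inside the window.

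On coverage, 4.4.1.1 says "A one-week delay in CAB LA dosing for the Q2M regimen at steady state is predicted to result in ~92% rather than 95"% of participants having CAB troughs above the PA-IC90, "which is considered acceptable". For RPV, 4.4.1.2 predicts a median trough about 11% lower after a one-week delay at steady state, "with >99% of subjects still remaining above the RPV" PA-IC90.

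The SAP sets the planned interval at 60 days (12.6.2) and the Q2M target day for Month m at 30(m−1)+1 (12.3.1). In 12.1.1, criterion 02, days beyond 67 between injections count as under-dosing time, and 10% or more of time on treatment is grounds for per-protocol exclusion. The same criterion names two or more intervals affected by over-dosage for the Month 12 analysis. Its examples include a gap under 7 weeks, with only split doses excepted.

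**The concern.** A site that follows the protocol exactly can leave a gap two weeks longer than planned, and nothing in the protocol asks it to call anyone. The text gives no prediction for such a gap, nor for a lengthened first interval after loading, when levels may not yet be at steady state. Section 6.8.1 links resistance risk to the time after drug levels fall below therapeutic values, so how long a gap may run without discussion matters.

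The two documents also do not line up. The protocol permits a gap of 68 to 74 days as compliant dosing, while the SAP books the excess over 67 as non-compliant time. At the short end, the SAP's 7-week item does not except the loading interval that the protocol orders. At stake are a missed safety prompt and a per-protocol rule that can flag correct dosing.

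**Working it through.** **The plan's own figures.** 60 + 7 = 67 days reproduces the SAP limit. For RPV, 1 − 48/54 = 11.1%, matching the stated 11%. A log-normal fit to the stated median of 54 ng/mL and 90% interval of 23 to 112 (log-SD 0.481) puts 99.8% above 12 ng/mL at a median of 48, consistent with over 99%. The CAB figure of 92% cannot be rebuilt, because the model is not given.

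**Inputs.** Target days for Months 2 to 12: 31, 91, 151, 211, 271, 331. Second injection offset −7 to 0; later offsets −7 to +7.

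**Permitted gaps** (next target + offset, minus previous target + offset):
- Loading: planned 31 − 1 = 30 days; permitted 24 − 1 = 23 up to 30.
- Month 2 to 4: shortest 84 − 31 = 53, longest 98 − 24 = 74.
- Later intervals: shortest 144 − 98 = 46, longest 158 − 84 = 74.
- Calendar months (assumption: two-month steps of 59 to 62 days): longest 73 to 76, shortest 45 to 48.

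**Counts of permitted date pairs.** Over 67 days: 28 of 8 × 15 = 120 for Month 2 to 4, and 28 of 15 × 15 = 225 for each later interval. Under 49 days: 0 of 120 and 6 of 225. These describe what the rule allows, with every date weighted equally. They say nothing about how often such gaps would occur.

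**One fully in-window schedule.** Days 1, 24, 98, 144, 218, 264, 338 give gaps of 23, 74, 46, 74, 46, 74. Under-dosing time is 3 × (74 − 67) = 21 days. Two post-loading gaps fall under 49 days, so the literal over-dosage count is met with no dose out of window.

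**Under-dosing share.** The denominator runs to the last on-treatment viral load (SAP 12.1.1). With a viral load at each injection visit, the worst in-window case is 21/338 = 6.2% to Month 12, and 7/98 = 7.1% if follow-up ends at Month 4. On calendar months these become 25/342 = 7.3% and 9/100 = 9.0%.

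**Over-dosage count.** Of 8 × 15⁵ = 6,075,000 in-window schedules to Month 12, 12,960 (0.2%) contain two or more post-loading gaps under 49 days and 635,040 (10.5%) contain at least one. The second figure is the share that would meet the two-interval count if the loading interval were also scored. Equal weighting applies here too.

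**Illustration only.** Assume a second week of delay has the same effect as the first. CAB coverage would then be about 88% (equal step on the probit scale) to 89% (92 − 3), and RPV about 99.6%. Neither is a prediction from the plan.

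**The case against.** The window is a reasoned choice. The Day 1 anchor prevents drift, no in-window dose is more than 7 days after its date, and 74 days requires the previous dose to have been 7 days early, so it is not a pure two-week delay. Section 4.4.1.2 cites similar flexibility in LATTE-2 and ATLAS-2M, 6.8.1 expects dosing in the week of the projected visit, and HIV-1 RNA is scheduled at every injection visit. All of this stands, and it is why the point is minor. The flexibility statement does, however, rest on the one-week prediction and does not address a longer gap.

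On the SAP, criterion 02 opens by requiring non-compliance, the 7-week item is an example, the study team reviews each case, and exclusion is a case-by-case clinical decision. A loading dose given as ordered was probably never meant to count, and it excludes nobody alone. This too stands; what remains is that the written example excepts split doses and nothing else.

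The protocol refers further dosing instructions to the Study Procedures Manual, which was not available. The absence of a limit is therefore a statement about the protocol and SAP only.

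**Conclusion.** The point holds as a minor one. The protocol permits, without a prompt, gaps up to 74 days on the SAP's 60-day interval (73 to 76 on calendar months). That is up to 7 days beyond both the 67 days at which the SAP starts counting under-dosing and the one-week delay for which the text gives a prediction. The SAP's 7-week example literally reaches protocol-ordered and in-window dosing. That effect is confined to the supportive per-protocol population, needs two intervals, and is likely rare. The ITT-E primary analysis is untouched.

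Four stronger readings are tempting, and the documents do not support them:
- That coverage at 74 days is inadequate. No prediction is given at that gap, in either direction.
- That the modelled delay is really 63 days, because the Figure 2 caption reads "for the Optimized CAB LA Q8W Regimen (600 mg IM Day 1, Week 4, Q8W Thereafter". The delay sentence itself refers to the Q2M regimen, so the caption alone does not settle it.
- That SAP Table 15 already limits the interval to 67 days. Its last-injection-plus-67 rule applies only to participants who permanently discontinue.
- That in-window dosing can never reach the 10% under-dosing limit. The shares above assume a viral load at each injection visit, and Protocol 12.10.1 allows injection visits without laboratory tests. Injections on Days 24 and 98 with the last viral load on Day 24 give 7/24 = 29%.

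**What to change.** 1. In footnote k (both copies), 4.2.2, 6.8.1 and 8.6.1, keep the Day 1 anchor and the ±7 days and add: *If an injection will be given more than 67 days after the previous one, contact the Medical Monitor beforehand, even if it is within the window.* The basis is 60 planned days plus the one week the text addresses, and agreement with the under-dosing limit in SAP 12.1.1. A 63-day trigger would catch a dose only 4 days late after an on-time one.
2. In SAP 12.1.1, apply the under-7-weeks item only to intervals after the second injection, and only when the later injection was given earlier than the protocol window allows.

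The cost is one sentence in the protocol, one clause in the SAP and an occasional extra call after an early injection. With calendar months, a dose at +6 or +7 days after an on-time injection can also trigger a call (62 + 6 = 68, 62 + 7 = 69). No dose is forbidden that is allowed now.

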8.1.2. Time and Events Table for DTG + RPV Administration

Procedures for DTG+RPV	Day 1 ^a	Month 3	Month 6	Month 9	Month 12	WD ^j	Notes
Written Informed Consent	X						
a. The Day 1 visit will take place during Week 312 (or Week 324 in the event of unavoidable delays) of the LATTE study, the participant's last week on study. LATTE participants eligible for POLAR study dosing will take final dose of CAB 30 mg + RPV 25 mg in the clinic. See Section 6.2 for dosing administration.
 
b. Physical exams should be conducted as part of normal routine clinical care but data will not be collected in the eCRF. Medical assessments include any decisions the study staff must make for participant management.
 
c. Measure vital signs after about 5 minutes of rest in a semi-supine position.
 
d. Height collected at Day 1 only.
 
e. On Day 1, ECGs should be performed in triplicate at least 5 minutes apart and following 5 minutes of rest in a semi-supine position within 1 hour prior to first dose. Also on Day 1, a 2-hour post dose ECG will be performed for all participants. The 2-hour post dose ECG on Day 1 can also be used for the LATTE Week 312 (or Week 324, if needed) visit. ECG evaluations at other visits should be obtained after dosing, preferably 2-4 hours post dosing.
 
f. Plasma for storage samples are collected for possible future analyses, back-up in cases of loss/damage in transit and geno/pheno analyses for virologic failures.
 
g. A (-) urine pregnancy test is required prior to any administration of drug and as required by medical monitor after a treatment interruption. A (+) urine test should be confirmed with a stat serum test. If (+), participant will need to be WD.
 
h. Fast overnight; however, a minimum of a 6 hour fast is acceptable.
 
i. DTG 50 mg + RPV 25 mg. Administer daily with food
 
j. Follow Up Visit - Conduct ~4 weeks after the last dose of IP and only if the participant has ongoing AEs or lab abnormalities at the last on-study visit. May be conducted by telephone.

Demography	X						
Eligibility Verification	X						
Physical Exam	X						
Medical History	X						
CDC Classification	X						
RPR	X						
Symptom Directed Physical Exam and Medical Assessment ^b		X	X	X	X	X	
Vital Signs (BP, HR) ^c	X	X	X	X	X	X	
Weight, Height & BMI ^d	X	X	X	X	X	X	
HIV Associated Conditions, AE and SAE Assessments, Con Meds	X	X	X	X	X	X	
12-Lead ECG ^e	X				X	X	
HIV-1 RNA	X	X	X	X	X	X	
CD4+	X	X	X	X	X	X	

Procedures for DTG+RPV	Day 1 ^a	Month 3	Month 6	Month 9	Month 12	WD ^j	Notes
Plasma for Storage ^f	X	X	X	X	X	X	
PK Sample for Storage						S	
Clinical Chemistry and Hematology	X	X	X	X	X	X	
Pregnancy Testing ^g	U	U	U	U	U	U	
Urinalysis	X					X	
Fasting: Glucose, Cholesterol (Total, HDL and LDL) and Triglycerides ^h	X					X	
PT/PTT/INR	X					X	
HIVTSQc					X	X	
HIVTSQs	X		X		X	X	
HIVDQoL	X		X		X	X	
Participant Visit Reminder Contact	X	X	X	X	X		
Participant Contact Detail Confirmation	X	X	X	X	X		
Study intervention Dispensation ⁱ	X	X	X	X	X		

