4.2. Treatment Groups and Duration

4.2.1. Eligibility for the POLAR Study for Participants Entering from the LATTE Study

Informed consent must be obtained prior to any study procedures, including any Day 1 assessment.

All participants with an undetectable HIV-1 RNA (<50 c/mL) at Week 300 in the LATTE study are eligible to enter this study. A single repeat to determine eligibility may be allowed ONLY after consultation with the medical monitor. Participants with HIV-1 RNA ≥ 200 c/mL at Week 300 are not eligible to enter the study and will not be allowed a repeat to determine eligibility. The Day 1 visit of the POLAR study will be performed in parallel with the final closeout visit for the LATTE study, Week 312 or (if contracts have not been finalized and/or institutional review board (IRB) approval has not been obtained by Week 312 in the LATTE study) Week 324.

Result of HIV-1 RNA at Week 300	Action
<50 c/mL	Begin POLAR study at Day 1
≥ 50 c/mL but <200 c/mL	Single repeat allowed only after consultation and approval from medical monitor
Single repeat <50 c/mL	Begin POLAR study at Day 1
Single repeat ≥ 50 c/mL	Cannot begin POLAR and must be withdrawn from the LATTE study; Complete withdrawal visit.
≥ 200 c/mL	Cannot begin POLAR and must be withdrawn from LATTE; Complete withdrawal visit.

Should a participant be allowed a repeat, results of this repeat must be available prior to Day 1 of this study, therefore the time needed for scheduling the Day 1 visit, lab draws and lab analysis should be considered.

In addition to the viral load criteria above, if in the opinion of the Investigator, a participant experiences a significant safety event while taking either CAB or RPV, study eligibility will be determined ONLY in consultation with the medical monitor.

Participants ineligible for this study will be withdrawn from LATTE.

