4.2.2.1. Participants electing to receive oral DTG + RPV once daily

The DTG + RPV oral regimen will be administered in an open-label fashion starting on Day 1 until Month 12. Participants will continue study intervention until:

- study intervention is locally approved and commercially available,
- the participant no longer derives clinical benefit,
- the participant meets a protocol-defined reason for discontinuation

Safety and efficacy assessments will be conducted as per the Time and Events schedule (Section 8.1 for more information). Dosing will occur according to the selected regimen.

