6.2. Treatment Assignment

Participants transitioning from the LATTE study on oral CAB + RPV treatment will transition to their elected treatment regimen, either Q2M administration of CAB LA + RPV LA or oral DTG + RPV single tablet regimen. Regardless of treatment arm, the

investigator should instruct all participants on the importance of treatment adherence. This study has an open-label design. Dosing is outlined in [Table 2](#).

Table 2 Dosage and Administration

Maintenance Phase (Day 1 to End of Study⁺)	
Q2M Arm- Transitioning from LATTE	
First Injections (Loading Doses) – Day 1 and Month 2	
Day 1	
 • Receive last dose of oral CAB + RPV regimen • Receive CAB LA 600 mg given as 1 X 3 mL IM injection • Receive RPV LA 900 mg given as 1 X 3 mL IM injection
Month 2	
 • Receive CAB LA 600 mg given as 1 X 3 mL IM injection • Receive RPV LA 900 mg given as 1 X 3 mL IM injection
Maintenance Injections – every 2 months (Q2M) following Month 2	
Month 4 to End of Study ⁺ (two 3 mL injections every 2 months)	
 • Receive CAB LA 600 mg given as 1 X 3 mL IM injection • Receive RPV LA 900 mg given as 1 X 3 mL IM injection
Oral DTG + RPV Arm – Transitioning from LATTE	
Day 1 to Month 12 ⁺ (once daily FDC tablet taken with food)	
 • Take one tablet of DTG 50 mg + RPV 25 mg once daily
+Until locally approved and commercially available, the participant no longer derives clinical benefit, the participant meets a protocol-defined reason for discontinuation or until development of CAB LA or RPV LA is terminated	

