#### 12.2.2. Protocol Defined Schedule of Events for DTG + RPV Administration

Procedures for DTG+RPV	Day 1 a	Month 3	Month 6	Month 9	Month 12	WD j	Notes
Written Informed Consent	Х						a. The Day 1 visit will take place during Week 312 (or Week 324 in the event of unavoidable delays) of the LATTE study, the
Demography	Х						participant's last week on study. LATTE participants eligible for POLAR study dosing will take final dose of CAB 30 mg + RPV 25
Eligibility Verification	Х						mg in the clinic. See Section 6.2 of the protocol for dosing administration.  b. Physical exams should be conducted as part of normal routine
Physical Exam	Х						clinical care but data will not be collected in the eCRF. Medical assessments include any decisions the study staff must make for
Medical History	Х						participant management. c. Measure vital signs after about 5 minutes of rest in a semi-supine
CDC Classification	Х						position. d. Height collected at Day 1 only.
RPR	Х						e. On Day 1, ECGs should be performed in triplicate at least 5 minutes apart and following 5 minutes of rest in a semi-supine position within 1 hour prior to first dose. Also on Day 1, a 2-hour
Symptom Directed Physical Exam and Medical Assessment b		Х	Х	Х	Х	Х	post dose ECG will be performed for all participants. The 2-hour post dose ECG on Day 1 can also be used for the LATTE Week 312 (or Week 324, if needed) visit. ECG evaluations at other
Vital Signs(BP, HR) °	Х	Х	Х	Х	Х	Х	visits should be obtained after dosing, preferably 2-4 hours post dosing.
Weight, Height & BMI d	Х	Х	Х	Х	Х	Х	f. Plasma for storage samples are collected for possible future analyses, back-up in cases of loss/damage in transit and geno/pheno analyses for virologic failures.
HIV Associated Conditions, AE and SAE Assessments, Con Meds	Х	Х	Х	Х	Х	Х	g. A (-) urine pregnancy test is required prior to any administration of drug and as required by medical monitor after a treatment interruption. A (+) urine test should be confirmed with a stat

I. Or Long-Term Follow Up

m. Follow Up Visit - Conduct ~4 weeks after the last dose of investigational product (IP) if not entering Long-Term Follow Up and only if the participant has ongoing AEs or lab abnormalities at the last on-study visit. May be conducted by telephone.

Procedures for DTG+RPV	Day 1 a	Month 3	Month 6	Month 9	Month 12	WD j	Notes
12-Lead ECG °	Х				Х	Х	serum test. If (+), participant will need to be WD. h. Fast overnight; however, a minimum of a 6 hour fast is

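### In the DTG + RPV arm, the Day 1 schedule note keeps a final in-clinic CAB + RPV dose although Section 4.2.2.1 and Table 2 start DTG + RPV that day; taken literally this is 50 mg oral RPV

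*Protocol*

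**What the plan says.** Note a to the Day 1 column of the DTG + RPV schedule (Protocol Section 8.1.2) reads "LATTE participants eligible for POLAR study dosing will take final dose of CAB 30 mg + RPV 25 mg in the clinic" and then refers the reader to Section 6.2. The same note appears in the schedule in Section 1.3. SAP Section 12.2.2 repeats it: "LATTE participants eligible for POLAR study dosing will take final dose of CAB 30 mg + RPV 25" (the sentence continues there as in the protocol).

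Section 4.2.2.1 sets the start of the new regimen: "The DTG + RPV oral regimen will be administered in an open-label fashion starting on Day 1 until Month 12". Table 2 in Section 6.2 has a row for this arm running from Day 1 to Month 12, with the instruction "Take one tablet of DTG 50 mg + RPV 25 mg once daily". The line "Receive last dose of oral CAB + RPV regimen" stands in Table 2 under the Q2M arm only.

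On the visit itself, Section 4.2.1 says "The Day 1 visit of the POLAR study will be performed in parallel with the final closeout visit for the LATTE study". The row "Study intervention Dispensation" in Section 8.1.2 is marked at Day 1. Note e asks for triplicate ECGs in the hour before the first dose and one ECG two hours after dosing, and adds: "The 2-hour post dose ECG on Day 1 can also be used for the LATTE Week 312 (or Week 324, if needed) visit".

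Section 6.9 treats more than 25 mg oral RPV in a day as an overdose. For DTG + RPV it has a separate rule based on the number of tablets.

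**The concern.** A site that reads note a gives CAB + RPV in the clinic on Day 1. A site that reads Section 4.2.2.1 or Table 2 starts the DTG + RPV tablet on Day 1. A site that follows all three gives both, and the participant takes two oral RPV doses in one day. Note a sends the reader to Section 6.2 for dosing, but Table 2 there gives this arm no last CAB + RPV dose.

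What is at stake is whether the dosing instruction can be carried out. As written, it cannot be followed in full within the protocol's own daily oral RPV dose, and different sites could reasonably choose different regimens for that day.

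**Working it through.** The plan gives no figure of its own on this point. The check is a sum and a comparison of passages.

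**Inputs**
- RPV in the final CAB + RPV dose: 25 mg (Protocol 8.1.2, note a).
- RPV in one DTG + RPV tablet: 25 mg (Protocol 6.2, Table 2).
- Total daily oral RPV dose above which an overdose is declared: 25 mg (Protocol 6.9).

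**Oral RPV on Day 1**
- Both instructions followed: 25 + 25 = 50 mg; 50 / 25 = 2.0 times the Section 6.9 dose, summing RPV across products.
- Either regimen alone: 25 mg; 25 / 25 = 1.0.
- Other limits in Section 6.9 with both followed: DTG + RPV tablets 1 of 1 and oral CAB 30 of 30 mg, so neither is exceeded.

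**Is the order of the two doses given anywhere?**
- Protocol 4.2.2, 6.8.1.1, 8.1.1 (note a) and 8.8.1 all place the last oral CAB + RPV dose relative to the injections or the pre-dose PK sample. All are written for the injection arm.
- Note a of the injection schedule has the same sentence plus a two-hour timing clause. The DTG + RPV note has the sentence without the clause. For an injection, an oral dose just beforehand is a stated part of the switch; for a tablet that also contains RPV, no such plan is described.
- Inclusion criterion 4 (Protocol 5.1) requires CAB + RPV up to Day 1, without saying whether Day 1 is included.

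**Which single reading fits the rest of the plan?**
- Note e times the pre-dose triplicate to a first dose on Day 1. In this arm the in-clinic CAB + RPV dose would be the last of its kind; the first dose of the new regimen is the DTG + RPV tablet.
- SAP Table 7, the baseline rule for this arm, excludes a 2-hour post-dose ECG taken on the treatment start date, and Table 13 does the same. Both expect that ECG and the treatment start to share a date.
- Section 4.2.2.1 and Table 2 say Day 1 directly.

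These agree on the first tablet being taken on Day 1. The sentence in note a is the one that does not fit.

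**The case against.** The best case on the other side is that this is loose wording which a sensible site would resolve. Day 1 in Section 4.2.2.1 and Table 2 can be read as the label of a treatment period. The schedule for this arm lists dispensation on Day 1, whereas the injection schedule lists administration. A coherent sequence is then: final LATTE dose in clinic, tablets handed over, first tablet the next day. No sentence tells anyone to take both, Section 6.9 itself would steer a site away from it, and the Study Procedures Manual, which is not among the documents, may give the order.

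Part of this stands. The manual could settle practice, and nothing shows that any participant took both doses or that sites differed. The next-day reading does not hold up as the plan's intent, though. It runs against the Day 1 start in Section 4.2.2.1, the first-dose timing in note e and the date logic of SAP Table 7. A supplementary manual should not have to override the protocol's dosing table.

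A reader might go further and infer a safety problem. The documents do not support that. The 50 mg counts as an overdose only if RPV is summed across products, and Section 6.9 does not make an overdose an adverse event without a clinical manifestation. The RPV doses that Section 2.3.1 links to QTc prolongation are 75 mg and 300 mg once daily. Nor does taking two integrase inhibitors on one day add much: Section 6.9 allows at least 5 days for oral CAB to become undetectable, so some overlap follows any direct switch.

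**Conclusion.** The Day 1 instruction for the DTG + RPV arm is wrong as written, and the point is minor. Its size is one day of dosing in one arm: 50 mg oral RPV instead of 25 mg if every instruction is followed. The number of participants in that arm is not stated. The conclusion rests on the protocol and SAP alone and on adding RPV across the two products. It claims no clinical harm. The primary endpoint is not affected: the primary objective concerns the injection regimen, and one day's difference in the first tablet does not bear on a Month 12 viral load.

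A reader might also infer that the QTc baseline is compromised, because a next-day start could let the 2-hour ECG count as a pre-treatment value. That needs two things the documents do not establish: that the first tablet was taken the next day, and that the in-clinic CAB + RPV dose was not entered on the exposure form from which SAP Section 12.6.1 takes the treatment start. Protocol Section 6.1 counts oral CAB and oral RPV as investigational product, so the second is open. Even if both held, no bias is shown. It is not part of this finding.

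**What to change.** Delete the sentence on the final CAB + RPV dose from note a in Protocol Sections 1.3 and 8.1.2 and SAP Section 12.2.2. In its place, state that the last CAB + RPV dose is taken the day before and the first DTG + RPV tablet on Day 1. In note e, state that the Day 1 pre-dose and 2-hour ECGs refer to the DTG + RPV tablet. Oral RPV on Day 1 is then 25 mg, and the text matches Section 4.2.2.1, Table 2 and the SAP baseline rule for this arm without other changes.

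The cost is a short amendment, which needs ethics approval under Section 12.2.1, and a matching edit to the SAP. The ECG shared with the LATTE close-out visit would follow DTG + RPV and not LATTE drug. That sharing is optional, so a separate LATTE ECG may be needed; the LATTE protocol, which is not available here, would decide.

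If the sponsor prefers to keep the in-clinic CAB + RPV dose, Section 4.2.2.1 and Table 2 should say that DTG + RPV starts the next day. The trade-off is that no scheduled ECG would then follow a DTG + RPV tablet until Month 12 or withdrawal. The documents do not say whether any Day 1 visits remain; if none do, the change only corrects the record.
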